7.2.3 Vital Signs

Vital sign measurements will include sitting systolic and diastolic blood pressure and heart rate and body temperature. Vital signs and sitting blood pressure and pulse rate should be measured after the patient rests for approximately 5 minutes and with the patient in a sitting position. The blood pressure measurement should be repeated after at least 30 seconds and the average of the 2 readings recorded.

7.3 Immunogenicity

7.3.1 Collection of Samples for Measurement of Antibodies to Metreleptin and Leptin and *In Vitro* Neutralizing Activity

Blood samples for the measurement of antibodies to metreleptin and human leptin will be collected at the times specified in the Study Plan (Table 1). A cell-based assay and a receptor-binding assay will be used to measure *in vitro* neutralizing activity in all samples that test positive for antibodies to metreleptin and/or leptin (titer ≥ 5). The study lab manual will provide specific instructions for collection, processing, packaging, and shipping of all samples.

Additional safety samples for measurement of antibodies to metreleptin and human leptin will be collected if clinically indicated (e.g., loss of response to MYALEPT, or if patient develops a severe infection and/or sepsis), or at the discretion of the Investigator. The date, time of collection, and results (values, units, and reference ranges) will be recorded on the appropriate eCRF.

7.3.2 Determination of Antibodies to Metreleptin and Leptin

A Receptor Binding Electrochemiluminescent Immunoassay (ECLIA) Procedure for the Detection of Neutralizing Antibodies to Metreleptin and Leptin in Human Serum has been developed and validated to detect antibodies to both endogenous leptin and metreleptin (this method was previously submitted and approved by the FDA as part of our post-marketing commitments).

Antibodies to metreleptin are detected using a bridging ELISA format method. Full details of this method will be described in a separate report.

Confidential Page 34 of 58

7.3.3 Determination of Metreleptin *In Vitro* Neutralizing Activity

There are no clinical indicators clearly associated with *in vitro* neutralizing activity; detection of neutralizing activity is achieved using an *in vitro* cell-based assay method. If no activity is detected upon initial testing with the cell-based assay, the result is reported as Category A. If activity is detected at the initial test concentration, the sample is retested at the same concentration, and if no activity is detected on retest, the initial result is attributed to assay noise, and the sample is reported as Category B. If activity is detected on both tests at initial concentration, the sample is diluted and retested until activity is no longer detected. Depending on the number of dilutions required to dilute activity below the detectable threshold, the result is reported as Category C, D, or E. Category D and E results are considered to represent high potency *in vitro* neutralizing activity. The clinical relevance of *in vitro* neutralizing activity results in any category has not been determined, and is a topic of current investigation.

In addition, the receptor binding Electro-chemiluminescence (ECLIA) Procedure for the detection of neutralizing Antibodies to Metreleptin and Leptin in Human Serum has been developed and validated to detect antibodies to both endogenous leptin and metreleptin (this method was previously submitted and approved by the FDA as part of Aegerion's post-marketing commitments). The results are reported as percent inhibition and 80% inhibition is currently utilized as the neutralizing antibody threshold.

7.4 Pharmacokinetics

No formal pharmacokinetic (PK) analyses of metreleptin will be conducted; leptin concentrations will be measured.

7.4.1 Collection of Samples for Measurement of Leptin

Blood samples for the measurement of leptin will be collected at the times specified in the Study Plan (Table 1). The centralized laboratory will provide specific instructions for collection, processing, packaging, and shipping of all samples.

Additional safety samples for measurement of leptin will be collected if clinically indicated (e.g., loss of response to MYALEPT, or if patient develops a severe infection and/or sepsis), or at the discretion of the Investigator. The date, time of collection, and results (values, units, and reference ranges) will be recorded on the appropriate eCRF.

Confidential Page 35 of 58

7.4.2 Determination of Leptin Concentration

Samples for determination of leptin concentration in plasma will be analyzed by a local laboratory using an appropriate bioanalytical method. Full details of the analytical methods used will be described in a separate bioanalytical report.

7.4.3 Storage and Destruction of Pharmacokinetic Samples

Any residual back-up PK samples may be used for future exploratory biomarker research or in the development of the ligand-binding assay. PK samples may be disposed of after finalization of the Bioanalytical Report, unless further analyses are necessary.

Incurred sample reproducibility analysis, if any, will be performed alongside the bioanalysis of the test samples. The results from the evaluation will not be reported in the Clinical Study Report but separately in a Bioanalytical Report.

7.5 Pharmacodynamics

Pharmacodynamic samples will not be evaluated in this study.

7.6 Pharmacogenetics

Pharmacogenetic samples will not be taken during the study.

7.7 Biomarker Analysis

No biomarkers, with the exception of those described in Table 1, will be analyzed.

8. SAFETY REPORTING AND MEDICAL MANAGEMENT

The Principal Investigator is responsible for ensuring that all staff involved in the study is familiar with the content of this section.

All adverse events, including SAEs, adverse events leading to discontinuation, and AESIs will be recorded on the eCRF. Additionally, all SAE and AESI that require immediate reporting will be captured on the SAE/AESI form and sent to the pharmacovigilance department (see Section 8.6).

Confidential Page 36 of 58

8.1 Definition of Adverse Events

An AE is the development of an undesirable medical condition or the deterioration of a pre-existing medical condition following or during exposure to a pharmaceutical product, whether or not considered causally related to the product. An undesirable medical condition can be symptoms (e.g., nausea, chest pain), signs (e.g., tachycardia, enlarged liver) or the clinically significant abnormal results of an investigation (e.g., laboratory findings). In clinical studies, an AE can include an undesirable medical condition occurring at any time, including run-in or washout periods, even if no study treatment has been administered.

8.2 Definitions of Serious Adverse Events

An SAE is an AE occurring during any study phase (i.e., run-in, treatment, wash-out, follow-up), that fulfills one or more of the following criteria:

- Results in death
- Is immediately life-threatening
- Requires in-patient hospitalization or prolongation of existing hospitalization
- Results in persistent or significant disability/incapacity or substantial disruption of the ability to conduct normal life functions
- Is a congenital abnormality or birth defect
- Is an important medical event that may jeopardize the patient or may require medical intervention to prevent one of the outcomes listed above

For further guidance on the definition of an SAE, refer to Appendix A.

In addition, for the purposes of this protocol, the following adverse events of special interest (AESI) must be handled as SAEs and are reportable to Aegerion or designee (see Section 8.6) within the SAE timeframe regardless whether the adverse events did not meet the serious criteria described above in this section:

- The presence of Category D or E *in vitro* neutralizing activity (or the relevant corresponding test result from the ligand-binding method) to metreleptin
- Necrotizing pancreatitis
- Hepatic adverse events including potential DILI

Confidential Page 37 of 58

- Severe hypoglycaemia
- Severe hypersensitivity reactions
- New diagnoses of autoimmune disorders (for instance, autoimmune hepatitis, glomerulonephritis, lupus erythematosus, antiphospholipid antibody syndrome, rheumatoid arthritis)
- Autoimmune disease exacerbation
- Serious infection resulting in hospitalization
- All cancers (excluding non-melanoma skin cancer) by cancer type
- Exposed pregnancies and pregnancy outcomes

8.3 Recording of Adverse Events

8.3.1 Time Period for Collection of Adverse Events

Adverse events (AE), including serious adverse events (SAE), AEs leading to discontinuation and AESIs will be recorded from the signing of the informed consent or if the AE or AESI is related to study procedure.

8.3.2 Follow-up of Unresolved Adverse Events

Any SAEs, AEs leading to discontinuation and AESIs that are unresolved at the patient's last assessment as appropriate in the study are followed up by the Investigator for as long as medically indicated, but without further recording in the eCRF. Aegerion retains the right to request additional information for any patient with ongoing AE/SAE(s) at the end of the study, if judged necessary.

8.3.3 Variables

The following variables will be collected for each AE leading to discontinuation and AESI:

- AE (verbatim)
- Date and time when the AE started and stopped
- Maximum intensity
- Maximum common terminology criteria for AE grade
- Whether the AE is serious or not

Confidential Page 38 of 58

- Investigator causality rating against metreleptin (yes or no)
- Action taken with regard to metreleptin
- AE led to patient's withdrawal from study (yes or no)
- Outcome

In addition, the following variables will be collected for SAEs:

- Date AE met criteria for SAE
- Date Investigator became aware of SAE
- Reason AE is serious
- Date of hospitalization
- Date of discharge
- Probable cause of death
- Date of death
- Autopsy performed
- Causality assessment in relation to study procedure(s)
- Description of AE

It is important to distinguish between serious and severe AEs. Severity is a measure of intensity whereas seriousness is defined by the criteria in Section 8.2. An AE of severe intensity need not necessarily be considered serious. For example, nausea that persists for several hours may be considered severe nausea, but not an SAE unless it meets the criteria presented in Section 8.2. On the other hand, a stroke that results in only a limited degree of disability may be considered a mild stroke but would be an SAE when it satisfies the criteria in Section 8.2.

Intensity rating scale to be used:

- Mild (awareness of sign or symptom, but easily tolerated)
- Moderate (discomfort sufficient to cause interference with normal activities)
- Severe (incapacitating, with inability to perform normal activities)

8.3.4 Causality Collection

The Investigator will assess causal relationship between metreleptin and each AE with the answer 'yes' or 'no' to the question 'Do you consider that there is a reasonable possibility that the event may have been caused by metreleptin?'

Confidential Page 39 of 58

The causal relationship will also be assessed for other medications and study procedures.

A guide to the interpretation of the causality question is provided in Appendix A.

8.3.5 Adverse Events Based on Signs and Symptoms

All adverse events, including SAEs, AEs leading to discontinuation, or AESIs spontaneously reported by the patient or care provider, or are reported in response to the open question from the study personnel or revealed by observation will be collected and recorded in the eCRF. When collecting AEs, the recording of diagnoses is preferred (when possible) over recording a list of signs and symptoms. However, if a diagnosis is known and there are other signs or symptoms that are not generally part of the diagnosis, the diagnosis and each sign or symptom will be recorded separately.

8.3.6 Adverse Events Based on Examinations and Tests

The results from protocol-mandated laboratory tests and vital signs will be summarized in the clinical study report. Deterioration, as compared to baseline, in protocol-mandated laboratory values and vital signs should be reported as.

8.3.7 Any new or aggravated clinically significant abnormal medical finding at a physical examination as compared with the baseline assessment should also be reported. Hy's Law

Cases where a patient has an AST or ALT $\ge 3x$ ULN and total bilirubin $\ge 2x$ ULN may need to be reported as SAEs. Refer to Appendix B for further instruction in cases of combined increase of aminotransferase and total bilirubin.

8.3.8 Adverse Events of Special Interest

Adverse events of special interest will be collected and recorded in the eCRF.

A sample should be collected for measurement of *in vitro* neutralizing activity in all patients with the following AEs of special interest: suspected loss of response (worsening of metabolic control) or suspected loss of endogenous leptin action (severe infections or sepsis).

For patients who become pregnant during the study, a sample should also be collected to measure *in vitro* neutralizing activity at the time the pregnancy is identified. The patient

Confidential Page 40 of 58

will be allowed to continue in the study; however, the decision as to whether to continue metreleptin therapy during the pregnancy will be at the discretion of the treating physician. The pregnancy and all pregnancy outcomes should be reported as an AESI and followed by the patients' prescribing physician.

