2.2 Rationale for Study Design, Doses and Control Groups

This study is being conducted to satisfy a postmarketing requirement to assess the immunogenicity associated with metreleptin treatment. Because immunogenicity can only be evaluated in the context of drug treatment, the study is open-label and will characterize antibody and *in vitro* neutralizing activity over time and will compare safety and tolerability in patients with different antibody statuses (e.g., binding antibody titer, *in vitro* neutralizing activity category, in vitro neutralizing activity percent inhibition). Immunogenicity will be evaluated in the context of the prescribing information for MYALEPT; thus, the patient population and dosing will be per the US prescribing information (MYALEPT Prescribing Information).

Anti-metreleptin and anti-HuL binding antibody titers over time will be evaluated in order to establish a time course of antibody development and to assess the development of antibodies that recognize the endogenous protein. Because samples from a few patients treated with metreleptin have demonstrated *in vitro* neutralizing activity in an *in vitro* cell-based assay, *in vitro* neutralizing activity will also be assessed in all antibody positive samples. To provide an orthogonal method to evaluate potential *in vitro* neutralizing activity, all antibody positive samples will also be assessed using a ligand-binding assay.

Safety and tolerability of metreleptin associated with the development of, or absence of, antibodies will be evaluated. All adverse events (AEs) will be collected throughout the course of this study. Serious adverse events (SAEs), adverse events of special interest

Confidential Page 17 of 60

(AESI) AEs leading to discontinuation, standard laboratory tests and vital signs will be collected over time and analyzed for any potential association with antibody status. See Section 8.2 for definitions of AEs and AESIs

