3.3 Safety Objectives

Safety Objectives: Outcome Measure:

Evaluate the safety and tolerability in relation to the development of or absence of anti-metreleptin or anti-huL antibodies, and/or *in vitro* neutralizing activity to metreleptin in patients with congenital or acquired generalized lipodystrophy.

Measure in vitro neutralizing activity in all

Measure *in vitro* neutralizing activity in all patients with suspected loss of response (worsening of metabolic control) or endogenous leptin action (severe infections or sepsis) at time of adverse event report.

SAEs, adverse events leading to discontinuation, loss of response (as assessed by HbA1c and serum triglycerides), severe infections and/or sepsis, standard laboratory tests, and vital signs over time.

Receptor-binding assay titer, cell-based assay category.

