6.3 Treatment Period

After the first dose of metreleptin is administered at Visit 2 (Month 0), patients will complete Visits 3 to 12 at Months 1, 2, 4, 6, 9, 12, 18, 24, 30, and 36. Descriptions of the procedures for this period are included in the Study Plan (Table 1); all procedures should be conducted prior to administration of metreleptin on the day of the study visit. The following will be conducted during the treatment period:

- Blood samples for measurement of leptin and antibodies to metreleptin and human leptin will be collected.
- Samples for measurement of HbA1c, lipids and fasting glucose will be collected.
- Fasting samples for hematology and clinical chemistry will be collected (only at Visits 6, 8, 9, 10, and 12).

Confidential Page 30 of 58

- Vital signs and weight will be measured.
- A physical examination, including height, will be conducted at Visits 8, 10, and 12.
- Concomitant use of lipid-lowering and antidiabetic, will be reviewed.
- Urine will be collected for urinalysis (only at Visits 8, 10, and 12).
- Urine pregnancy tests (βhCG) will be conducted for all female patients of childbearing potential.
- Serious adverse events and AESI (refer to Section 8.3.8) will be reviewed.

All Visit 12 assessments should be conducted for patients who discontinue the study prior to Month 36.

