#### 17.1 Adverse Events

Adverse Events (AEs) will be coded using the latest version of MedDRA, and summarized by SOC, preferred name, and intensity. Intensity is captured in the CRF. See **Section 8.1** Statistical Tests and Confidence Intervals for a description of summaries to be reported.

Adverse Events of Special Interest (AESIs) are defined as:

- The presence of Category D or E *in vitro* cell-based NAb activity (or the relevant corresponding test result from the ligand-binding method) to metreleptin
- Necrotizing pancreatitis
- Hepatic adverse events including potential drug induced liver injury (DILI)
- Severe hypoglycemia
- Severe hypersensitivity reactions
- New diagnoses of autoimmune disorders (for instance, autoimmune hepatitis, glomerulonephritis, lupus erythematosus, antiphospholipid antibody syndrome, rheumatoid arthritis)
- Autoimmune disease exacerbation
- Serious infection resulting in hospitalization
- All cancers (excluding non-melanoma skin cancer) by cancer type
- Exposed pregnancies and pregnancy outcomes.

TEAEs are defined as AEs that started or worsened in severity on or after the first dose of study medication. If it is unclear whether or not an AE is a TEAE due to partial dates, the worst case will be assumed (i.e., TEAE). See **Appendix 1** for handling of partial dates.

AEs, serious AEs (SAEs), AEs of special interest (AESIs), TEAEs, AEs possibly caused by metreleptin, and AEs leading to metreleptin discontinuation will be summarized by ADA positivity and titer, cell-based NAb positivity and titer, and RB positivity, titer, and quintile of percent

Document: Statistical Analysis Plan: AEGR-734-401: A 36-Month, Multicenter, Open Label Phase 4 Study to Evaluate the

Immunogenicity of Daily SC Metreleptin Treatment in Patients with Generalized Lipodystrophy

Author: [name], [name], [name], [name] Version Number: 2.1

inhibition. For each patient, only one event of each type will be selected to include in summary outputs. If a patient has multiple events the same type, the event with the highest severity level is selected. For patients with multiple events of the same type and severity, the event corresponding to the highest titer or percent inhibition level is selected. The corresponding titer and percent inhibition level are defined by the most recent measurement occurring prior to the event start date.

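### Suspected loss of response, and severe infection without hospitalization, are AESIs in Protocol 8.3.8 but fall outside the AESI definition in Protocol 8.2 and SAP 17.1, so the AESI-by-antibody tables cannot show them

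*Protocol*

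**What the plan says.** - **Protocol 8.3.8** requires a neutralizing-activity sample in all "patients with the following AEs of special interest", and then names them: "suspected loss of response (worsening of metabolic control) or suspected loss of endogenous leptin action (severe infections or sepsis". There is no condition on hospitalization. Pregnancy is also to be reported as an AESI.
- **Protocol 8.2** lists ten AESIs and puts them on the SAE reporting timeline. The only infection item is "Serious infection resulting in hospitalization". No item mentions response, metabolic control, HbA1c or triglycerides.
- **Cross-references within the protocol point both ways.** Section 2.2 says "See Section 8.2 for definitions of AEs and AESIs". Sections 4.11.1, 6.2.2 and 6.3 point to 8.3.8; for example, 6.3 says "Serious adverse events and AESI (refer to Section 8.3.8) will be reviewed".
- **SAP 17.1** states that "Adverse Events of Special Interest (AESIs) are defined as" and repeats the ten items of Protocol 8.2. It tabulates AESIs, along with other classes of adverse event, by binding-antibody (ADA), cell-based neutralizing (NAb) and receptor-blocking (RB) status. The December 2024 change limits these tables to TEAEs. Its visible text does not touch the AESI list.
- **Protocol 3.3** includes among its safety outcome measures "loss of response (as assessed by HbA1c and serum triglycerides), severe infections and/or sepsis, standard laboratory tests, and vital signs over time".

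**The concern.** Protocol 2.1 names loss of metreleptin efficacy and inhibition of endogenous leptin as the potential consequences of neutralizing antibodies. The same section says that the postmarketing requirement behind this study includes an analysis of clinical events associated with binding or neutralizing antibodies. A reader will look for that link first in the AESI tables by antibody status.

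Under the SAP definition, those tables have no place for loss of response and only a partial place for infection. They could appear to show no association between neutralizing activity and loss of response simply because no such event can enter them.

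**Working it through.** The point rests on definitions, and the plan states no figure to reproduce. The check has three steps.

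**1. Compare the lists.**

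| Event | Protocol 8.3.8 | Protocol 8.2 | SAP 17.1 |
|---|---|---|---|
| Suspected loss of response | AESI | not listed | not listed |
| Severe infection or sepsis, hospitalized and serious | AESI | listed | listed |
| Severe infection or sepsis, not hospitalized | AESI | not listed | not listed |
| Pregnancy | AESI | listed | listed |

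Protocol 8.2 and SAP 17.1 share the same 10 items: 0 of 10 cover loss of response, and 1 of 10 covers infection, in part. The infection gap is not just wording, because Protocol 8.3.3 distinguishes severe (intensity) from serious (the 8.2 criteria).

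**2. Follow one event through the tables.** Take worsening metabolic control that is not serious, in a patient who stays on drug. After the December 2024 change, five classes are tabulated by antibody status:

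- TEAEs: included, if recorded as an adverse event.
- Serious TEAEs: not included.
- TEAEs that are AESIs: not included under the SAP list.
- TEAEs possibly caused by metreleptin: probably not included. Protocol Appendix A tells the investigator to answer no to causality when the disease under study worsens through lack of effect.
- TEAEs leading to discontinuation: not included.

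The event therefore appears in 1 of 5 classes (2 of 5 if judged related), under whatever preferred term was coded.

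**3. Look for the outcome elsewhere.** Protocol 10.5 plans two analyses that would fill the gap:

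- a summary of maximum titers and neutralizing activity with associated clinical events, including loss of efficacy;
- change in HbA1c and percent change in triglycerides by peak titer and by neutralizing activity.

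Neither is in the visible SAP sections 15 to 18. SAP 18.2 summarizes HbA1c and triglycerides by visit, as change from baseline and in categories, with no antibody stratum. The SAP does not define loss of response. Yet SAP 4.3 declares no changes from the protocol, and SAP section 2 says the SAP prevails where methods differ.

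**Size, for illustration.** The documents give no rate for these events. With the 11 patients of SAP 4.1, one such patient is 1/11 = 9% and two are 2/11 = 18%.

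**The case against.** Several points on the other side are sound.

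- **Collection is not limited to SAEs and AESIs.** A reader might infer from 6.3 that sites look for nothing else. It does not say so, and it refers to 8.3.8, the section with the wider wording. Protocol 2.2, 8 and 8.3.5 and Table 1 provide for collecting all adverse events. The detailed list in 8.3.3 opens with "The following variables will be collected for each AE leading to discontinuation and AESI", and it would apply to these events if 8.3.8 governs.
- **The events are not lost from all antibody output.** A reader might infer that both outcomes vanish. They do not. TEAEs are tabulated by the same antibody strata, adverse events are also summarized by intensity, and serious infections with hospitalization stay in the AESI tables. What is lost is identification, completely for loss of response and partly for infection.
- **The protocol sections can perhaps be read together.** Section 8.2 may list only the AESIs needing expedited reporting, with 8.3.8 as a sampling trigger; section 8 speaks of AESIs that require immediate reporting. But 2.2 names 8.2 as the place where AESIs are defined. Even if this reading were right, SAP 17.1 would have taken the narrower list as its whole definition.
- **HbA1c and triglycerides are measured at every visit.** They are, but the visible SAP never relates them to antibody status.

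It also remains open whether AESIs are flagged on the CRF or derived from the SAP list. If they are flagged, some 8.3.8 events could still enter the tables. The table shells and parts of the SAP change form were not available for this check, so a later correction cannot be excluded.

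**Conclusion.** The inconsistency is real and should be fixed. Under the SAP definition the AESI tables by antibody status contain no loss-of-response events and no severe infections without hospitalization. The Protocol 10.5 summaries that would have covered loss of efficacy are missing from the visible SAP. An outcome named in the safety objective is therefore never identified by antibody status.

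This is a gap in identification and reporting. The documents do not show that data went uncollected or that the events are absent from the general TEAE tables, so it falls short of a defect that must be corrected before any result can be used. The 9% to 18% is an assumed range, not an expected rate. The conclusion assumes that AESI tables follow the SAP 17.1 list and that no later change altered it.

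**What to change.** 1. Reconcile Protocol 8.2 and 8.3.8, and state whether the 8.3.8 events follow the SAE reporting route. Simply adding them to the 8.2 list would settle that by default, because its items are to be handled as SAEs. No position is taken here on the answer.
2. Under SAP 17.1, add two separate rows by ADA, NAb and RB status: suspected loss of response; and severe infection or sepsis, whether or not hospitalized.
3. Identify cases by medical review of the adverse event records, preferably without sight of the antibody results. Triggered-sample records can help to locate cases but cannot define them, because samples are also taken for pregnancy (8.3.8) and at investigator discretion (7.3.1).
4. Restore the Protocol 10.5 summaries: titers and neutralizing activity with loss of efficacy, and HbA1c and triglycerides by peak titer and neutralizing activity. Otherwise, record their omission under SAP 4.3.
5. Label the output as a post-database-lock addition where that applies. The SAP change form dated 26 February 2025 already records changes made after lock.

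The cost is some wording, two table rows, the restored summaries and a review of about 11 patients' records. The downside is a few events to classify and a little more table work.
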